## SECTION 1. ABSTRACT

---

### Objective

To evaluate the effect of continuing treatment with caffeine citrate in the hospital and at home in moderately preterm infants with resolved apnea of prematurity on days of hospitalization after randomization.

### Study Design

Randomized, 1:1 allocation with parallel enrollment, double-blinded, placebo-controlled, multicenter trial.

### Primary Outcome

The primary outcome of the study will be the number of days of hospitalization from randomization to discharge up to 48 weeks post-menstrual age (PMA), with censoring at time of transfer or death.

### Secondary Outcomes

The secondary outcomes of the study will be:

- a. The number of days to physiologic maturity after randomization up to 48 wks PMA.

Physiologic maturity will be defined as follows:

- i. Temperature: out of the incubator for at least 48 hours with normal body temperature
- ii. Feeding: oral feeding at a volume of at least 140 ml/kg/day or growing on less than 140 ml/kg/day for at least 48 hours
- iii. Respiratory: apnea-free for at least 5 consecutive days

- b. Post menstrual age at discharge up to 48 wks PMA, censoring at time of transfer or death (status).
- c. The number of all cause readmissions, including apneic events and apparent life-threatening events (ALTE), to the hospital within the first four weeks, second four weeks, and first eight weeks combined after discharge from the hospital by 48 wks PMA.
- d. The number of all cause sick visits to urgent care, emergency room or health care provider office within the first four weeks, second four weeks, and first eight weeks combined after discharge from the hospital by 48 wks PMA.
- e. Safety outcome measures pre-hospital discharge
  - Weight gain from randomization until status (discharge up to 48 wks PMA, with censoring at time of transfer or death). The weight gain may also be assessed using percentiles including birthweight percentiles.
  - The number of days after randomization until status that infant had at least two consecutive heart rates >200 documented at least 3 hours apart (when infant not crying).

- Treatment for high blood pressure initiated after randomization until status.
- The number of episodes between randomization and status that infant was placed NPO for  $\geq$  24 hours.
- The use of anti-reflux medications started between randomization and status
- The number of days that significant apnea/bradycardia, as defined by documentation of infant receiving any of the following between randomization and status: open label caffeine, other methylxanthines, doxapram, CPAP or ventilatory support for apnea/bradycardia.
- The presence of documented and treated arrhythmias between randomization and status, not due to tachycardia or bradycardia.
- The onset of documented seizures, as defined by treating with anti-convulsants, between randomization and status.

f. Death

Evaluation of infants during the first four weeks, second four weeks, and first eight weeks combined after discharge from the hospital is done to determine whether there is a difference in post-discharge secondary outcomes on caffeine (first four weeks), off caffeine (second four weeks), and in overall outcomes after discharge home (first eight weeks).

A short discussion on the hypothetical cost-savings by the reduction in number of days of hospitalization as a financial benefit of the trial's intervention (caffeine versus placebo) will be added to the discussion section of the manuscript at the conclusion of the trial.

## Eligibility Criteria

### Inclusion Criteria

Inborn and outborn infants of  $29^{0/7}$  to  $33^{6/7}$  weeks gestational age at birth admitted to hospitals of the National Institute of Child Health and Human Development Neonatal Research Network (NRN)  $\leq$  72 hours of age and who at time of enrollment are:

- a.  $33^{0/7}$  -  $35^{6/7}$  weeks post-menstrual age at the time of randomization
- b. Receiving caffeine with plan to discontinue treatment or just discontinued caffeine treatment
- c. Receiving feeds at a volume of  $\geq$ 120 ml/kg/day by oral and/or tube feeding
- d. Ability to start study medication within 72 hours after stopping caffeine

### Exclusion Criteria

- a. On respiratory therapy (oxygen more than room air equivalent for high altitude sites, nasal cannula, continuous positive pressure ventilation, and/or mechanical ventilation).
- b. Infants who would otherwise be discharged home on apnea monitor due to underlying disease or family history, including history of a sibling with sudden infant death syndrome
- c. Parental request for apnea monitor
- d. Congenital heart disease other than atrial septal defect, ventricular septal defect, or patent ductus arteriosus

- e. Neuromuscular conditions affecting respiration
- f. Major congenital malformation and/or genetic disorder
- g. Plans to transfer to a non-NRN site before discharge
- h. Unable to obtain parental or guardian consent

### **Study Intervention/Methods**

Study subjects will be patients in the NICU at one of the participating hospitals at a Neonatal Research Network site. Infants who meet the eligibility criteria will be randomized to either caffeine citrate at 10 mg/kg/dose (5 mg/kg caffeine base) or a placebo (equal volume of all the excipients except for the active ingredient, caffeine citrate) to be given daily, not less than 12 hours between doses, beginning within 72 hours of open label caffeine discontinuation. The infant may still require hospitalization for observation after discontinuation of open label caffeine or for other discharge issues such as temperature control or feeding tolerance.

Infants who will continue caffeine citrate or placebo at home for the first 28 days after hospital discharge, will have a weight obtained within 48 hours of discharge to be used for dosage calculation. On the day of discharge, the parent will be supplied with 28 numbered vials with oral caffeine citrate (intervention group) or placebo at an equivalent volume (placebo group). Oral syringes will be provided to the parents to draw up doses. The parents will be educated by the research nurse, discharge nurse, physician, or pharmacist on storage and administration of study medication. A member of the research team will contact the parents to obtain post-discharge information within 72 hours after discharge, once a week for the first 4 weeks, and biweekly during the weeks 5 to 8 after discharge.

### **Sample Size**

To obtain a two-day difference in the outcome of median number of days of hospitalization after randomization, from 14 days to 12 days, with a power set at 90%, a significance of 0.05, and an attrition of 5%, the trial would require 587 infants per group for a total of 1174 infants. At 80% power, the trial would require 479 infants per group for a total of 878 infants. The minimum required sample size for this trial will be 878 (439 in each treatment group), but enrollment will continue until either the presently-acquired supply of study drug is exhausted or expires in approximately August 2023 (accounting for full in-hospital and post-discharge follow-up), whichever comes first. The Neonatal Research Network gathers data on approximately 3000 moderately preterm infants a year, with approximately 1000 treated with caffeine.

Effect Size (days)	Significance	Power (%)	Attrition (%)	Sample Size
14 to 10	0.05	80	5	226
14 to 10	0.05	90	5	302
14 to 12	0.05	80	5	878
14 to 12	0.05	90	5	1174

## **SECTION 2. CONFLICT OF INTEREST DISCLOSURES**

---

Per Title 42, Code of Federal Regulations, Part 50, Subpart F (50.604 Responsibilities of Institutions regarding Investigator financial conflicts of interest), as amended, institutions and all sub-recipients are required to notify the grants officer of any financial conflicts of interest (FCOI) prior to expenditure of any funds and within 60 days of any subsequently identified FCOI.

## **SECTION 3. STATEMENT OF PROBLEM**

---

### **3.1. HYPOTHESES**

#### **3.1.1. Primary Hypothesis**

The primary hypothesis is that in moderately preterm infants with resolved apnea of prematurity (AoP), continuing caffeine treatment compared to placebo will decrease the number of days of hospitalization from randomization to discharge up to 48 weeks post-menstrual age (PMA), with censoring at time of transfer or death. AoP is a leading cause of prolonged hospitalization in these infants and, therefore, it is expected that caffeine therapy will shorten hospitalization.

#### **3.1.2. Secondary Hypotheses**

In moderately preterm infants with resolved AoP, continuing caffeine therapy for 28 days after hospital discharge compared to placebo will:

- a. decrease the number of days to reach physiologic maturity from randomization to discharge up to 48 wks PMA.
- b. decrease the number of readmissions to the hospital related to apneic or apparent life-threatening events as well as all-cause readmissions within the first four weeks, second four weeks, and first eight weeks combined after discharge from the hospital by 48 wks PMA.
- c. decrease the number of sick visits related to apneic or apparent life-threatening events as well as all-cause sick visits to urgent care, emergency rooms, or health care providers within the first four weeks, second four weeks, and first eight weeks combined after discharge from the hospital by 48 wks PMA.
- d. be safe for continuing caffeine during the hospitalization and after discharge home without an increase in side effects or adverse events
- e. decrease the number of days of hospitalization from randomization to discharge, leading to a hypothetical cost-savings as a financial benefit of the trial's intervention

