#### **3.1.4. Secondary Specific Aims**

- a. To evaluate the effect of continuing treatment with caffeine citrate in the hospital on number of days to reach physiologic maturity from randomization to discharge up to 48 wks PMA.

- b. To evaluate the effect of treatment with caffeine until 28 days after hospital discharge on all-cause readmissions to a hospital (including apneic and/or apparent life-threatening events) within the first 8 weeks after discharge by 48 wks PMA.
- c. To evaluate the effect of treatment with caffeine until 28 days after hospital discharge on the number of all-cause sick visits to urgent care, emergency rooms, or health care provider's office (including apneic and/or apparent life-threatening events) within the first 8 weeks after discharge by 48 weeks PMA.
- d. To evaluate the side effects and adverse events of caffeine continuation in the hospital and after discharge up to 4 weeks post study drug administration.
- e. To assess the hypothetical cost-savings by the reduction in number of days of hospitalization as a financial benefit of the trial's interventions.

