### 4.2. SECONDARY OUTCOMES

The secondary outcomes of the study will be:

- a. The number of days to physiologic maturity after randomization up to 48 wks PMA.  
Physiologic maturity will be defined as follows:
  - i. Temperature: out of the incubator for at least 48 hours with normal body temperature
  - ii. Feeding: oral feeding at a volume of at least 140 ml/kg for 48 hours or growing on less than 140 ml/kg/day for at least 48 hours
  - iii. Respiratory: apnea-free for at least 5 consecutive days
- b. Post-menstrual age (PMA) at discharge up to 48 wks PMA, censoring at time of transfer or death (status).
- c. The number of all-cause readmissions, including apneic events and apparent life-threatening events (ALTE), to the hospital within the first four weeks, second four weeks, and first eight weeks combined after discharge from the hospital by 48 wks PMA.  
An apparent life-threatening event is defined by the American Academy of Pediatrics as an event that is perceived by the observer as life-threatening. This event can include apnea, color change (cyanosis), profound change in muscle tone (hypotonia), gagging, and/or choking.
- d. The number of all-cause sick visits, urgent care, emergency rooms, or health care provider's office, within the first four weeks, second four weeks, and first eight weeks combined after discharge from the hospital by 48 wks PMA.
- e. Safety measures pre-hospital discharge
  - a. Weight gain from randomization until status (discharge up to 48 wks PMA, with censoring at time of transfer or death). The weight gain may also be assessed using percentiles including birthweight percentiles.
  - b. The number of days after randomization until status that infant had at least two consecutive heart rates >200 documented at least 3 hours apart (when infant not crying).
  - c. Treatment for high blood pressure initiated after randomization until status.
  - d. The number of episodes between randomization and status that infant was placed NPO for  $\geq 24$  hours.
  - e. The use of anti-reflux medications started between randomization and status
  - f. The number of days that significant apnea/bradycardia, as defined by documentation of infant receiving any of the following between randomization and status: open label caffeine, other methylxanthines, doxapram, CPAP or ventilatory support for apnea/bradycardia.

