In addition, the following data will be obtained from the family during follow-up calls and from returned mailed-in forms:

- Infant weights at all health care provider visits (well child and sick visits)
- Reasons for sick visits to the Health Care Provider, urgent care, or emergency room
- Reasons for admission to the hospital
- Final diagnosis when discharged from the hospital

A member of the research staff will be available during the day (8 am to 5 pm) for questions regarding the study medication and trial. If the infant requires medical attention, it should be addressed by the Health Care Provider or emergency medical care staff. The evaluating physician should treat the patient's medical needs, regardless of the involvement in the trial. Once the patient is stable, if the physician or parent/guardian requires further information related to the trial, a member of the research team may be contacted. Information obtained from the trial is unlikely to change the immediate care of the patient if sick.

Expedited serious adverse events will be reported per local IRB guidelines, and to the NICHD and NRN Data Coordinating Center at RTI.

The trial will record side effects and any study related serious adverse events will be reported to the DSMC periodically. Expedited serious adverse events will be reported per local IRB guidelines, and to the NICHD and the NRN Data Coordinating Center at RTI. All protocol deviations and violations will be reported.

The following detail describes the action to be taken for each adverse event below:

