## 9.2 Efficacy Variables

Primary and secondary efficacy variables are described in the table below.

| Variable                               | Type  | Definition   |  |
|--|-------|--|--|
| Primary Outcome                        |       |  |  |
| Number of days of hospitalization      | Count | The number of days between randomization and hospital discharge. This outcome is censored at 48 weeks PMA and at time of transfer or death   |  |
| Secondary Outcomes                     |       |  |  |
| Number of days to physiologic maturity | Count | Physiologic maturity is defined:  i. Temperature: out of the incubator for at least 48 hours with normal body temperature  ii. Feeding: oral feeding at a volume of at least 140 ml/kg for 48 hours or growing on less than 140 ml/kg/day for at least 48 hours  iii. Respiratory: apnea-free for at least 5 consecutive days  This outcome is censored at 48 weeks PMA. |  |

| Variable  | Type       | Definition  |
|---|------------|---|
| Number of days to physiologic maturity - Temperature                        | Count      | Physiologic maturity is defined:  i. Temperature: out of the incubator for at least 48 hours with normal body temperature  This outcome is censored at 48 weeks PMA.  |
| Number of days to
physiologic maturity –
Feeding                      | Count      | Physiologic maturity is defined:  i. Feeding: oral feeding at a volume of at least 140 ml/kg for 48 hours or growing on less than 140 ml/kg/day for at least 48 hours  This outcome is censored at 48 weeks PMA.            |
| Number of days to
physiologic maturity -
Respiratory                  | Count      | Physiologic maturity is defined:  i. Respiratory: apnea-free for at least 5 consecutive days This outcome is censored at 48 weeks PMA.  |
| Post-menstrual age at discharge   | Continuous | The post-menstrual age of the infant at discharge censored at 48 weeks PMA and at time of transfer or death   |
| Number of all-cause
readmissions within first 4
weeks post-discharge  | Count      | Number of hospital readmissions including apneic events and apparent life-threatening events during first 4 weeks following hospital discharge. The outcome is censored at 48 weeks PMA.                                    |

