| Number of all-cause
readmissions within second 4
weeks post-discharge | Count      | Number of hospital readmissions including apneic events and apparent life-threatening events during second 4 weeks following hospital discharge. The outcome is censored at 48 weeks PMA.                                   |
| Number of all-cause
readmissions within first 8
weeks post-discharge  | Count      | Number of hospital readmissions including apneic events and apparent life-threatening events during first 8 weeks following hospital discharge. The outcome is censored at 48 weeks PMA.                                    |
| Number of all-cause sick visits within first 4 weeks post-discharge         | Count      | Number of all cause sick visits, urgent care, emergency room, or other non-scheduled/routine health care provider office visits during first 4 weeks following hospital discharge. The outcome is censored at 48 weeks PMA. |
| Number of all-cause sick visits within second 4 weeks post-discharge        | Count      | Number of all cause sick visits, urgent care, emergency room, or other non-scheduled/routine health care provider office visits during last 4   |

| Variable  | Type        | Definition  |
|---|-------------|---|
|   |             | weeks following hospital discharge. The outcome is censored at 48 weeks PMA.  |
| Number of all-cause sick visits within first 8 weeks post-discharge | Count       | Number of all cause sick visits, urgent care, emergency room, or other non-scheduled/routine health care provider office visits during first 8 weeks following hospital discharge. The outcome is censored at 48 weeks PMA. |
| All-cause Mortality   | Categorical | Demise of Infant  |

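### Secondary hypotheses b and c name apnea/ALTE-related readmissions and sick visits, but every efficacy outcome is all-cause, so the hypothesised decrease gets no planned estimate by randomised arm

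*Protocol*

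**What the plan says.** **Hypotheses.** Protocol 3.1.2 b states that continued caffeine will "decrease the number of readmissions to the hospital related to apneic or apparent life-threatening events as well as all-cause readmissions". Item c states that it will "decrease the number of sick visits related to apneic or apparent life-threatening events as well as all-cause sick visits". Both apply to the first four weeks, the second four weeks and the eight weeks together after discharge.

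**Aims and outcomes.** The protocol's secondary aim b concerns "all-cause readmissions to a hospital (including apneic and/or apparent life-threatening events", with the apnea part in brackets. Protocol 4.2 c counts "The number of all-cause readmissions, including apneic events and apparent life-threatening events (ALTE), to the hospital". Item d counts all-cause sick visits and does not mention apnea. The abstract and SAP 3.1.2 and 3.2.2 follow the same pattern.

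**SAP efficacy variables.** SAP 9.2 has six post-discharge counts: readmissions and sick visits, each in three windows. The eight-week rows read "Number of hospital readmissions including apneic events and apparent life-threatening events during first 8 weeks following hospital discharge" and "Number of all cause sick visits, urgent care, emergency room, or other non-scheduled/routine health care provider office visits during first 8 weeks". No row counts apnea/ALTE-related events alone. SAP 9.4 models the listed outcomes, and SAP 13 declares no change from the protocol.

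**Where apnea-related events do appear.** The interim safety rule (Protocol 6.3.3, SAP 7.4) uses sick visits, emergency visits, ALTE episodes or hospitalizations tied to apnea of prematurity (AoP). It flags an increase on caffeine at p < 0.0158. Protocol 6.3.1 makes apnea/ALTE-related hospitalizations and visits serious adverse events, to be collected for eight weeks after discharge.

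**Data.** The follow-up data in Protocol 6.3.1 include "Reasons for admission to the hospital", reasons for sick visits, and final diagnoses.

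**The concern.** The hypotheses name two targets, joined by wording that makes the second additional to the first. The outcome lists keep one. Following the plan as written gives an all-cause estimate and nothing, as efficacy, for the apnea-related part.

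That part is the stated reason for treating at home. Protocol 3.3, 3.4 and 4.5.3 argue that home caffeine may reduce admissions and visits caused by apnea, and 3.4 undertakes to find out whether it reduces apneic episodes after discharge. Protocol 5.2.3 rules out home-monitor recordings as a data source, so visits and admissions attributed to apnea are the main post-discharge evidence on that question. No efficacy variable isolates them.

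Timing also matters. SAP 11 and 13 label analyses prompted by the final data as post hoc. An apnea-specific result could then carry that label although the protocol hypothesised it.

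**Working it through.** The point rests mainly on a comparison of text. No figure in the plan needs reproducing.

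**Step 1: trace each target.**

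| Target | Hypothesis (Protocol 3.1.2) | Protocol aims and outcomes | SAP 9.2 |
|---|---|---|---|
| All-cause readmissions, 3 windows | yes (b) | yes | 3 rows |
| All-cause sick visits, 3 windows | yes (c) | yes | 3 rows |
| Apnea/ALTE-related readmissions, 3 windows | yes (b) | only as part of the total | none |
| Apnea/ALTE-related sick visits, 3 windows | yes (c) | not as a separate count | none |

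The break occurs inside the protocol, between its hypotheses and its aims and outcomes. The SAP carries it over.

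**Step 2: ask whether the safety analyses fill the gap.**

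- *Interim rule.* It looks only for an increase on caffeine, uses a composite, and serves the monitoring committee. It is not a final analysis of benefit. It is also unclear whether the qualifier about AoP applies to the whole list or only to hospitalizations.
- *SAP 10.2.* Every safety variable ends at in-hospital status. None is post-discharge.
- *SAP 10.1.* Incidence is compared by chi-squared or Fisher's exact test, according to treatment received, with no windows.
- *SAP 10.3 and 10.4.* Events are summarised by type and treatment group, and serious events only if there are enough of them. The SAP's definition of a serious event does not name apnea-related visits, so an apnea-related office visit need not qualify.

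None of these estimates the hypothesised decrease by randomised arm in the three windows.

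**Step 3: illustrate dilution.** The documents give no rates, so every rate here is an assumption.

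Let *s* be the apnea-related share of all-cause events and let caffeine halve only those:

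- all-cause ratio = 1 − 0.5 × *s*
- *s* = 0.10: 0.95; *s* = 0.30: 0.85; *s* = 0.40: 0.80
- apnea-specific ratio = 0.50 throughout

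**Step 4: illustrate precision.** Further assumptions: 5-10% of placebo infants have at least one readmission, and *s* is 10-40%. The same rule is applied to risks, so apnea-related placebo risk = all-cause risk × *s*. Evaluable infants per arm are 439 × 0.95 ≈ 417 and 587 × 0.95 ≈ 557. Power is for a two-sided 0.05 comparison of two proportions, normal approximation, counting only results in the hypothesised direction.

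| Per arm | All-cause risk | Share | Power, apnea-specific | Power, all-cause |
|---|---|---|---|---|
| 417 | 5% | 10% | 9% | 4% |
| 417 | 10% | 40% | 40% | 17% |
| 557 | 5% | 10% | 10% | 4% |
| 557 | 10% | 40% | 50% | 21% |

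At 417 per arm, the expected number of placebo infants with an apnea-related readmission runs from 417 × 0.05 × 0.10 ≈ 2 to 417 × 0.10 × 0.40 ≈ 17. With so few events the approximation is rough. It shows that the all-cause comparison is a poor stand-in for the apnea-specific one, and that neither is well powered.

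**The case against.** **The events are analysed after all.** A reader might infer that the SAP looks only at all-cause counts and that the cause-specific hypotheses go wholly unexamined. The documents do not support that. AoP-related events are the formal interim safety outcome, and apnea/ALTE-related events are serious adverse events to be reported. The comparison in SAP 10.1 states no direction, so a decrease could show there. This stands, but Step 2 shows why it does not supply the missing estimate.

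**The SAP did not depart from the protocol.** Correct. The SAP reproduces the protocol's own aims and outcomes. Aligning the hypothesis wording would also remove the inconsistency, so the fix offers that option.

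**All-cause is a defensible choice.** Definitions of apnea are local, post-discharge reasons come from families, and Protocol 3.4 lists inaccurate or missing information on readmissions and sick visits as a known challenge. All-cause counts avoid attribution and capture net harm. This is a good reason to keep them, but it does not explain hypothesising something that is then not estimated.

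**The mechanism may be broader.** It is tempting to say that caffeine can act only on apnea-related events. Protocol 3.3 describes effects on the respiratory muscles, and 4.5.3 describes fewer desaturations and regards these as relevant regardless of apnea. The supportable statement is that apnea is the stated rationale for home treatment.

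**Little can be learned.** SAP 7.7 makes secondary p-values descriptive, counts will be sparse, and the shares in the illustration are invented. All true. It limits what the added rows can show.

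**Conclusion.** The point holds in a limited form. Half of each of hypotheses b and c has no efficacy variable, and no planned analysis by randomised arm estimates the hypothesised decrease. This follows from the text and needs no assumed rates.

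The size of the loss cannot be fixed from the documents. Under the assumed 10-40% share and a halving confined to apnea-related events, the all-cause ratio would be 0.95-0.80 when the apnea-specific ratio is 0.50. Sparse counts would leave both estimates imprecise.

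A reader might infer that the added analysis would confirm or refute the hypothesis. It would not: the p-values would be descriptive and the power low. The gain is a pre-specified, interpretable estimate in place of a safety tally or a post hoc result. The primary outcome is unaffected. The change should be made, and it is worth most if made before unmasking.

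**What to change.** **Preferred change**

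- Add to SAP 9.2, as secondary outcomes with descriptive p-values, the number of apnea/ALTE-related readmissions and the number of apnea/ALTE-related sick visits in weeks 1-4, 5-8 and 1-8 after discharge (six rows). Add matching entries to the protocol outcomes.
- Write an attribution rule based on recorded reasons and final diagnoses, and apply it before unmasking. Use the same rule to settle whether the AoP qualifier in SAP 7.4 covers the whole list.
- Analyse the ITT population by randomised arm with the count model used for the all-cause outcomes. If counts are too sparse for site adjustment, fall back on a simpler comparison named in advance, such as the proportion of infants with at least one event, by exact test.
- Keep the all-cause counts as they are.

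**Alternative.** If the rows are not added, delete the cause-specific half of hypotheses b and c.

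**Cost.** Six SAP rows, a short attribution rule, and masked classification of data already collected. The downsides are sparse counts, wide intervals and some misclassification from parent-reported reasons. The alternative costs only a wording change but gives up the stated question about home treatment.
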